Patients who meet all of the following inclusion criteria during the screening period will be eligible for enrolment in this study:

- 1. Age between 18 and 55 years, inclusive.
- 2. Diagnosis of relapsing forms of multiple sclerosis using revised McDonald criteria (Polman et al., 2011).
- 3. Stable on any FDA-approved disease modifying therapy (DMT). The term "stable" implies that the subject has not had change in therapy for any reason for the six months prior to study entry.
- 4.
- 5. EDSS 0 6.0 inclusive (Kurtzke, 1983).
- 6. Understood and signed written informed consent, obtained prior to the study subject undergoing any study-related procedure, including screening tests.

Exclusion Criteria

Patients who meet any of the following exclusion criteria during the screening period will not be eligible for enrollment in this study:

- 1. Known hypersensitivity to sulfonamides or derivatives
- 2. Known history of renal or hepatic disease, cerebrovascular disease including stroke, transient ischemic attack, myocardial infarction, angina or congestive heart failure
- 3. Evidence to suggest hyponatremia or hypokalemia, marked kidney dysfunction defined as creatinine greater than 2.0 mg/dL or liver disease dysfunction defined as aspartate aminotransferase (AST) or alanine aminotransferase (ALT) greater than three-fold upper limit of normal (ULN).
- 4. Evidence to suggest suprarenal gland failure.
- 5. Evidence of hyperchloremic acidosis.
- 6. Initiation of new immunosuppressant treatment after the subject becomes protocol-eligible (except for corticosteroids) or enrolment in a concurrent trial.
- 7. Prior treatment with mitoxantrone, natalizumab, rituximab, methotrexate, cladribine, cyclophosphamide or within 6 months of initiation of study.
- 8. Subjects with any history of cytopenia.
- 9. History of pulmonary obstruction or emphysema.
- 10. Active hepatitis B or hepatitis C infection or evidence of cirrhosis.

- 11. Human immunodeficiency virus (HIV) positivity.
- 12. Uncontrolled diabetes mellitus defined as HbA1c > 8% and/or requiring intensive management.
- 13. Uncontrolled viral, fungal, or bacterial infection (excluding asymptomatic bacteriuria).
- 14. Any condition that, in the opinion of the investigators, would jeopardize the ability of the subject to tolerate treatment with ACZ.
- 15. Prior history of malignancy.

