- 16. Positive pregnancy test or inability or unwillingness to use effective means of birth control. Effective birth control is defined as:
 - Refraining from all acts of vaginal intercourse (abstinence)
 - Consistent use of birth control pills
 - Tubal sterilization or male partner who has undergone vasectomy
 - Placement of an IUD (intrauterine device)
 - Use, with every act of intercourse, of a diaphragm with contraceptive jelly and/or condoms with contraceptive foam
- 17. Presence of metallic objects implanted in the body that would preclude the ability of the subject to safely have MRI exams.
- 18. Psychiatric illness, mental deficiency, or cognitive dysfunction making compliance with treatment or informed consent impossible.

Withdrawal Criteria

Patients can be withdrawn at any time if the investigator concludes that it would be in the patients' best interest for any reason. Patients may voluntarily withdraw from the study for any reason at any time. They may be considered withdrawn if they state an intention to withdraw, or fail to return for visits, or become lost to follow up for any other reason. Protocol violations should not lead to patient withdrawal unless they indicate a significant risk to the patient's safety. If premature patient withdrawal occurs for any reason, the principle investigator must determine the primary reason for a patient's premature withdrawal from the study and record this information on the Unanticipated Problems Tracking Log.

For patients who are lost to follow-up (i.e., those patients whose status is unclear because they fail to appear for study visits without stating an intention to withdrawal), the investigator will show "due diligence" by documenting in the source documents steps taken to contact the patient, e.g., dates of telephone calls, registered letters, etc. In the case of death, a patient will be considered withdrawn.

Subject Replacement

Patients who prematurely withdraw will not be replaced.

TRIAL SCHEDULE

Visit Schedule:

Stage 1a – IV ACZ in MS Subjects											
Total of 10 subjects (5 healthy and 5 MS patients)											
	Day -7	0 min	15 min	30 min	120 min	240 min					
	Screen										
Treatment		1 gm	1 gm IV bolus ACZ administered								
		immedia									
H&P	Х										
CBC, CMP	Х										
Urine pregnancy	Х										
pCASL MRI		Х	Х	Х	Х	Х					
DSC MRI						Х					

Stage 1b –Oral ACZ dose-escalation in MS Subjects											
Up to a Total of 10 subjects											

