Long-term studies in animals to evaluate the carcinogenic potential of acetazolamide have not been conducted. In a bacterial mutagenicity assay, acetazolamide was not mutagenic when evaluated with and without metabolic activation. The drug had no effect on fertility when administered in the diet to male and female rats at a daily intake of up to 4 times the recommended human dose of 1000 mg in a 50 kg individual.

Pregnancy: Teratogenic Effects: Pregnancy Category C

Acetazolamide, administered orally or parenterally, has been shown to be teratogenic (defects of the limbs) in mice, rats, hamsters and rabbits. There are no adequate and well-controlled studies in pregnant women. Acetazolamide should be used in pregnancy only if the potential benefit justifies the potential risk to the fetus.

Nursing Mothers

Because of the potential for serious adverse reaction in nursing infants from acetazolamide, a decision should be made whether to discontinue nursing or to discontinue the drug taking into account the

importance of the drug to the mother.

Description of Oral ACZ Drug Product

Manufactured by: Emcure Pharmaceuticals USA, Inc. [name]

Distributed by: Zydus Pharmaceuticals USA Inc. Princeton, NJ 08534

Repackaged by: American Health Packaging Columbus, Ohio 43217

Package Insert ACETAZOLAMIDE- acetazolamide capsule, extended release American Health Packaging

Acetazolamide Extended-Release Capsules

Rx Only

DESCRIPTION

Acetazolamide extended-release capsules are an inhibitor of the enzyme carbonic anhydrase.

Acetazolamide is a white to faintly yellowish white crystalline, odorless powder, weakly acidic, very slightly soluble in water and slightly soluble in alcohol. The chemical name for acetazolamide is N-(5-Sulfamoyl-1,3,4-thiadiazol-2-yl)acetamide and has the following chemical structure:

MW 222.24

C4H6N4O3S2

Each acetazolamide extended-release capsule intended for oral administration contains 500 mg of acetazolamide. In addition, each capsule contains the following inactive ingredients: ammonio methacrylate copolymer dispersion type A and B, FD&C yellow #6, gelatin, microcrystalline cellulose, sodium lauryl sulfate, talc and titanium dioxide. The capsule is printed with black pharmaceutical ink which contains black iron oxide as a coloring agent.

CLINICAL PHARMACOLOGY

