Caution is advised for patients receiving concomitant high-dose aspirin and acetazolamide, as anorexia, tachypnea, lethargy, metabolic acidosis, coma, and death have been reported.

PRECAUTIONS

General

Increasing the dose does not increase the diuresis and may increase the incidence of drowsiness and/or paresthesia. Increasing the dose often results in a decrease in diuresis. Under certain circumstances, however, very large doses have been given in conjunction with other diuretics in order to secure diuresis in complete refractory failure.

Information for Patients

Adverse reactions common to all sulfonamide derivatives may occur: anaphylaxis, fever, rash (including erythema multiforme, Steven-Johnson syndrome, toxic epidermal necrolysis), crystalluria, renal calculus, bone marrow depression, thrombocytopenic purpura, hemolytic anemia, leukopenia, pancytopenia, and agranulocytosis. Caution is advised for early detection of such reactions and the drug should be discontinued and appropriate therapy instituted.

In patients with pulmonary obstruction or emphysema where alveolar ventilation may be impaired, acetazolamide which may precipitate or aggravate acidosis should be used with caution. Gradual ascent is desirable to try to avoid acute mountain sickness. If rapid ascent is undertaken and acetazolamide is used, it should be noted that such use does not obviate the need for prompt descent if severe forms of high altitude sickness occur, i.e., high altitude pulmonary edema (HAPE) or high altitude cerebral edema.

Caution is advised for patients receiving concomitant high-dose aspirin and acetazolamide, as anorexia, tachypnea, lethargy, metabolic acidosis, coma, and death have been reported (see WARNINGS).

Both increases and decreases in blood glucose have been described in patients treated with acetazolamide. This should be taken into consideration in patients with impaired glucose tolerance or diabetes mellitus.

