Sulfonamides may give false negative or decreased values for urinary phenolsulfonphthalein and phenol red elimination values for urinary protein, serum non-protein, and serum uric acid. Acetazolamide may produce an increased level of crystals in the urine.

Acetazolamide interferes with the HPLC method of assay for theophylline. Interference with the theophylline assay by acetazolamide depends on the solvent used in the extraction; acetazolamide may not interfere with other assay methods for theophylline.

Carcinogenesis, Mutagenesis, Impairment of Fertility

Long-term studies in animals to evaluate the carcinogenic potential of acetazolamide has not been conducted. In a bacterial mutagenicity assay, acetazolamide was not mutagenic when evaluated with and without metabolic activation.

The drug had no effect on fertility when administered in the diet to male and female rats at a daily intake of up to 4 times the recommended human dose of 1000 mg in a 50 kg individual.

Pregnancy Teratogenic Effects Pregnancy Category C:

Acetazolamide, administered orally or parenterally, has been shown to be teratogenic (defects of the limbs) in mice, rats, hamsters, and rabbits. There are no adequate and well-controlled studies in pregnant women. Acetazolamide should be used in pregnancy only if the potential benefit justifies the potential risk to the fetus.

Nursing Mothers

Because of the potential for serious adverse reactions in nursing infants from acetazolamide, a decision should be made whether to discontinue nursing or to discontinue the drug taking into account the importance of the drug to the mother. Acetazolamide should only be used by nursing women if the potential benefit justifies the potential risk to the child.

Pediatric Use

The safety and effectiveness of acetazolamide extended-release capsules in pediatric patients below the age of 12 years have not been established. Growth retardation has been reported in children receiving long-term therapy, believed secondary to chronic acidosis.

Geriatric Use

Metabolic acidosis, which can be severe, may occur in the elderly with reduced renal function.

In general, dose selection for an elderly patient should be cautious, usually starting at the low end of the dosing range, reflecting the greater frequency of decreased hepatic, renal, or cardiac function, and concomitant disease or other drug therapy.

ADVERSE REACTIONS

Body as a whole:

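### The visible eligibility, contraception and screening text does not address nursing, although both package inserts in the protocol warn of potential serious reactions in nursing infants

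*Combined protocol and SAP*

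**What the plan says.** Section 3.4 (Exclusion Criteria) lists 18 exclusions. Number 16 removes women with a "Positive pregnancy test or inability or unwillingness to use effective means of birth control" and then defines acceptable contraception. Number 14 is the catch-all, for any condition that the investigators believe "would jeopardize the ability of the subject to tolerate treatment with ACZ". Section 6.2 (Contraception and Pregnancy Testing) repeats the birth-control rule for the length of the study and adds urine pregnancy tests. The screening visits for all stages list history, examination, blood tests and a pregnancy test.

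Nursing appears in the visible text only in the package inserts under Trial Materials. The Nursing Mothers paragraph of the IV insert opens with the reason for concern, "Because of the potential for serious adverse reaction in nursing infants from acetazolamide", and asks for a decision to give up either nursing or the drug. The oral extended-release insert says the same and adds: "Acetazolamide should only be used by nursing women if the potential benefit justifies the potential risk to the child".

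**The concern.** The study enrols women aged 18 to 55 with a disease that the protocol says is diagnosed in women nearly four times as often as in men. Some candidates may be nursing. Treatment ranges from one IV bolus in Stage 1a to as much as 48 weeks of oral ACZ in Stage 3.

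The oral insert's condition is a benefit-risk judgement, and the benefit side is weak here. The rationale section states that, to the authors' knowledge, ACZ has not previously been evaluated as a therapy in MS. The Stage 1a schedule also lists five healthy subjects, who have no disease for the drug to treat. What is at stake is infant safety: a woman could be dosed without the decision that both inserts ask for.

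**Working it through.** The check is textual, apart from one clearance calculation in step 4.

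**Step 1. Where a nursing rule could sit.**

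| Place | What it covers | Nursing addressed? |
|---|---|---|
| Inclusion criteria (3.3) | Age, diagnosis, stable therapy, EDSS, consent; item 4 is blank | Not in the visible items |
| Exclusions 1 to 18 (3.4) | Includes pregnancy and birth control (16) | No |
| Contraception and Pregnancy Testing (6.2) | Birth control, urine tests | No |
| Visit schedules and screening visits, all stages | History, examination, blood tests, pregnancy test | No |
| Specific Restrictions; Concomitant therapy | Over-the-counter products, aspirin, stable MS therapy | No |
| IV and oral inserts (Trial Materials) | Nursing Mothers paragraphs | Yes |

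**Step 2. Whether an existing rule catches the case indirectly.**

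- A pregnancy test does not identify a nursing woman, and she can satisfy any of the birth-control options in exclusion 16.
- Exclusion 14 concerns the subject's own tolerance of ACZ, not a risk to her child.
- The recruitment history is aimed at cardiovascular disease and glaucoma. The fuller Stage 3 history might reveal nursing, but no rule says what follows.
- End Points - Safety says that subjects receive the insert's list of adverse events with the consent form. The nursing warning sits under Precautions, outside the Adverse Reactions list. An adverse-event list is in any case not an eligibility rule.

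**Step 3. How similar insert text was handled.** For pregnancy both inserts use nearly the same benefit-risk wording: "Acetazolamide should be used in pregnancy only if the potential benefit justifies the potential risk to the fetus". That risk is covered by exclusion 16. For impaired ventilation the oral insert says only that "acetazolamide which may precipitate or aggravate acidosis should be used with caution". This is a caution, not a contraindication, yet exclusion 9 reads "History of pulmonary obstruction or emphysema". Being less than a contraindication therefore did not keep a topic out of the criteria.

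**Step 4. Clearance after the last dose.** The Stage 3 rationale gives a half-life of 60 to 75 hours and expects insignificant levels by two weeks. Assuming first-order elimination, the fraction remaining is 0.5^(t / half-life), with t = 14 × 24 = 336 h.

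- Half-life 60 h: 336/60 = 5.60 half-lives; 0.5^5.60 = 2.1% remaining.
- Half-life 75 h: 336/75 = 4.48 half-lives; 0.5^4.48 = 4.5% remaining.

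This agrees with the protocol's two-week statement and says nothing about transfer into milk. Neither insert gives a half-life. The 60 to 75 hours is stated for the Stage 3 capsules, so using it for the Stage 1a bolus would be an assumption. The oral insert describes 18 to 24 hours of action per dose. That is not the same quantity, but it is a reason not to lean hard on the half-life.

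**The case against.** Part of the relevant text cannot be seen. Consent pages were removed, inclusion item 4 is blank, and the protocol assigns discussion of risks to the consent process, with re-consent for later stages. The inserts are themselves in the protocol, they ask for an individual decision, and nursing is not a contraindication in either. The investigator who judges eligibility is also the treating physician and could make that decision. All of this is fair. It limits the point to the visible text and rules out calling the omission a breach of the label. It does not close the gap, because a rule about who may be dosed belongs in the criteria.

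Three stronger readings are tempting and are not supported.

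- *The protocol turns insert cautions into exclusions as a matter of course, so nursing is an anomaly.* It does not. The interactions with phenytoin, primidone, lithium, quinidine and cyclosporine have no exclusion, high-dose aspirin gets advice and a warning, and diabetes is excluded only when uncontrolled. The pregnancy paragraphs also report animal teratogenicity, whereas the nursing paragraphs give no data. Step 3 shows only that a caution can become a criterion.
- *A nursing rule must extend beyond the last dose.* Residual drug in the mother does not establish exposure or harm in the infant, and the inserts set no interval after dosing.
- *Inclusion 3 makes nursing candidates rarer.* It requires that "the subject has not had change in therapy for any reason for the six months prior to study entry". The documents do not say that nursing women change therapy, and the rule has no evident bearing on healthy Stage 1a subjects.

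**Conclusion.** The point holds as a limited safety gap worth closing. The visible rules would admit a nursing woman with a negative pregnancy test who meets the other criteria, and no visible step requires the decision that both inserts call for. The same applies to a healthy Stage 1a volunteer, for whom no separate criteria are visible.

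Its size cannot be stated. The documents give neither the number of nursing candidates, which is probably small, nor any figure for infant exposure. The conclusion assumes that the unseen consent pages and inclusion item 4 do not already handle nursing. If they do, the sponsor need only confirm it and align the criteria. Endpoints, sample size, power and analysis are unaffected.

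**What to change.** Add to exclusion 16: *currently nursing and unwilling to stop while on study drug (ACZ or placebo)*. Repeat it as a continuing rule in section 6.2 beside the birth-control rule. Ask all women about nursing at the screening visit of every stage, including Stage 1a. In Stage 3 apply the rule identically in both arms, with no arm-specific check at week 24, so that the blind is not touched. A woman may still take part if she chooses to stop nursing, which is the choice the inserts describe.

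The sponsor may also add a two-week wait before nursing resumes, following its own clearance statement. This would be a precaution that the documents do not require. It would need no new visit: Stage 3 (week 50, drug stopped at week 48) and Stage 2a (week 14, drug stopped at week 12) already have one two weeks after the last dose. The other stages would need an instruction at the last visit.

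The cost is one phrase, one sentence and one question. A few potential participants may be lost. In Stage 3, women who receive placebo first would also forgo nursing during those 24 weeks, which the blind makes unavoidable.

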CBC, CMP		Х	Х	Х	Х	Х	Х	Х	Х	X	
Urine pregnancy*		Х									
DSC MRI		Х		Х		Х		Х		Х	
pCASL MRI		Х	х	Х	Х	Х	X	Х	Х	X	Х
MSFC		Х	Х	Х	Х	Х	Х	Х	Х	Х	Х
EDSS		Х	Х	Х	Х	Х	Х	Х	Х	Х	Х
MFIS, MSWS-12		Х	х	Х	Х	Х	Х	Х	Х	X	Х
Blood Sample		X	х	Х	Х	X	Х	X	Х	X	Х
* Female par	rticipants v	who have alrea	ady beer	n evalua	ted for pi	regnancy	y will not	be retes	ted unle	ss otherwise	

* Female participants who have already been evaluated for pregnancy will not be retested unless otherwise indicated

- Additional CBC,CMP will be performed if measured ALT/AST > 1X ULN or if other alterations above baseline
- EDSS Expanded disability status scale
- MSFC Multiple Sclerosis Functional Composite Scale

STUDY DESIGN

Summary of Study Design

The initial stages of this study are designed as a proof of principle to show that ACZ therapy improves cerebral perfusion in MS subjects. The final stage of this study is a prospective crossover design to evaluate the potential for ACZ to persistently enhance cerebral perfusion and impact the evolution of T2 hyperintense MS lesions into permanent black holes. This pilot study is anticipated to lead to a larger randomized phase 3 clinical trial.

Participants will be recruited from the MS patient population seen at the UTP practice. The MS Clinic is a National MS Society affiliated comprehensive and coordinated center for MS care and a member of the Consortium of MS Centers. This clinic evaluates approximately 2700 MS patients per year. Given the safety and tolerability of study drug, we anticipate recruitment of two MS subjects each month for all stages of this study.

Stage 1a - This stage will determine the degree of change, temporal kinetics and difference between various regions in cerebral perfusion after IV ACZ in subjects with MS.

In total, this portion of the study is anticipated to be complete within 2.5 months. ACZ therapy and all image acquisition will be completed on the same day for subjects enrolled in stage 1a.

As all subjects will be treated with IV ACZ, the image analyst will be unblinded during this stage. Cerebral perfusion measures will be determined by S.D.

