Stage 1b - Participants in this stage of the study will be given escalating divided doses of oral ACZ up to 4000 mg per day to determine both the magnitude of change to cerebral perfusion with maintenance daily oral ACZ therapy and to define the optimum dose(s) for additional studies. Stage 1b and 2 of the study will utilize extended release oral ACZ, distributed by Hermann Research pharmacy and self-administered by the subject.

r	500mg BID	1000 mg BID	1500 mg BID	2000 mg BID	_	Legend + MPL pCASI
W -1	w o	W 2	W 4	W 6	W 8	+ MSFC + EDSS
Screening	+	÷	+	+	+	
	±	‡	+ *	+ +	+ *	

Treatment and data collection for stage 1b will take 2.5 months for each enrolled subject. As many as two subjects can be evaluated during the month and we would anticipate that this portion of the study can be completed within twelve months.

Image analysis will be performed once each subject completes treatment. Cerebral perfusion measures will be determined for each dose by the same unblinded analyst (S.D.).

Stage 2a - This stage will continue to gather information about whether daily oral ACZ is tolerated and the kinetics of the treatment effect. Patients continue on the same dose for 12 consecutive weeks and undergo repeat imaging at predetermined intervals. Sustained treatment over a short duration will allow us to rapidly determine whether sustained treatment with ACZ can alter cerebral blood flow and will provide a go/no-go for future studies using this drug/paradigm. Patients will obtain MRI scans and clinical evaluations every 6 weeks with contrast-based scans repeated at 12 weeks.

Stage 2b - This stage will determine long-term tolerability and if tachyphylaxis is present with oral ACZ. Patients will continue on the same dose for 24 consecutive weeks and undergo repeat imaging at predetermined intervals. MRI scans and clinical evaluations will be obtained every 6

weeks with contrast-based scans repeated every 12 weeks.

Stage 3 - This stage is a prospective delayed-start design to evaluate the potential for ACZ to persistently enhance cerebral perfusion and impact the evolution of MS lesions. This pilot study is anticipated to lead to a larger randomized phase 3 clinical trial.

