Subjects will obtain both contrast-enhanced and non-contrast MRI to fully evaluate both existing and newly formed MS lesions. In addition, contrast based analysis of cerebral perfusion offers measurements of CBV and MTT of blood, data not available with pCASL alone. DSC techniques will provide information that cannot be obtained by using pCASL alone that might be important to determine how blood flow is altered with ACZ.

Subjects will be randomized to either ACZ or placebo first. Both subjects and raters (both clinical and imaging) will be blinded to treatment arm. Image analysis will be performed at the end of study. Each subject scan will be assigned a random five-digit number. Experienced imaging analysts (I.V., S.D., L.F.), blinded to treatment arm, will obtain manual and semi-automatic quantitative measures of global and regional cerebral blood flow, T2 lesion volume, T1 lesion volume, T1-gadolinium (Gd) positive lesion volume, gray and white matter volume and global and regional atrophy. We will compare quantitative imaging measures between treatments. **METHODS AND ASSESSMENTS**

Patient recruitment, consenting and database procedures – All subjects for the study will be specifically recruited from the Neurology clinic located in the UTP building. Recruitment of all subjects will initially be sequential, based upon planned follow-up visits to the Neurology Clinic. Subsequent adjustments to patient recruitment might be introduced based upon periodic evaluation of evolving data that might dictate a more focused approach within certain patient groups. We anticipate that patient volunteers can be identified and consented on the day of their regularly scheduled Neurology Clinic visit. Thus, the first level of potential bias in the subjects studied will simply be that of the stochastic nature of the scheduled visits. However, there may be additional selection characteristics placed on recruitment of patient volunteers for the studies, should age or gender characteristics of the MS patients not be well reflected in the accumulating group.

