MRI scans for each subject will be assigned a unique non-contiguous random ID using a 5-digit random number generator and all imaging raters (I.V., S.D., L.F.) will be blinded to treatment arm. A semi-automated, previously validated tissue segmentation software (FreeSurfer v5.3, https://surfer.nmr.mgh.harvard.edu/) will be used to determine T2 hyperintense (lesion) and T1 hypointense (black hole) volumes. A separate expert rater (K.H.) will review and analyse DTI images. An expert rater (I.V), blinded both to treatment arm and sequence of scan acquisition, will perform quality control checks of software segmentation.

Image analysis to determine regional and global CBF as well as atrophy will be performed by additional qualified expert raters (S.D., L.F., K.H.) who are blinded to the treatment arm.

Contraception and Pregnancy Testing

Female participants must use effective means of birth control for the duration of the study. Effective birth control is defined as refraining from all acts of vaginal intercourse (abstinence), consistent use of birth control pills, tubal sterilization or male partner who has undergone vasectomy, placement of an IUD (intrauterine device), or use of a diaphragm with contraceptive jelly and/or condoms with contraceptive foam with every act of intercourse. Study participants will receive urine pregnancy tests prior to ACZ and as scheduled in the trial schedule (see section 4).

Study Visits and Procedures

Stage 1a:

Screening Visit – Subjects will receive a complete medical and neurological examination. In addition, all subjects will obtain CBC, CMP and, if female, urine pregnancy test.

Subjects will receive non-contrast MRI brain with scout, 3DT1 and pCASL sequences immediately prior to infusion of IV ACZ. The scout sequence is used to establish proper subject orientation and slice prescription and requires less than 5 minutes. The 3DT1 is a rapid sequence that allows for proper registration between scans and will be obtained after the scout images and again if the patient is removed from the MRI gantry. Finally, pCASL sequences will be performed to determine CBF. The group of sequences including pCASL will collectively require about 12 minutes.

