In those unusual instances where adequate control is not obtained by the twice-a-day administration of acetazolamide extended-release capsules, the desired control may be established by means of acetazolamide (tablets or parenteral). Use tablets or parenteral in accordance with the more frequent dosage schedules recommended for these dosage forms, such as 250 mg every four hours, or an initial dose of 500 mg followed by 250 mg or 125 mg every four hours, depending on the case in question.

Acute Mountain Sickness:

Dosage is 500 mg to 1000 mg daily, in divided doses using tablets or extended-release capsules as appropriate. In circumstances of rapid ascent, such as in rescue or military operations, the higher dose level of 1000 mg is recommended. It is preferable to initiate dosing 24 to 48 hours before ascent and to continue for 48 hours while at high altitude, or longer as necessary to control symptoms.

HOW SUPPLIED

Acetazolamide Extended-Release Capsules, 500 mg are white to off-white pellets filled in empty hard gelatin capsules with orange opaque cap imprinted with "EP" in black ink and white opaque body imprinted with "107" in black ink and are supplied as follows:

Unit dose packages of 30 (3x10) NDC 68084-401-21

Storage and Drug Accountability

Acetazolamide tablets will be stored at room temperature (between 68°F to 77°F) as suggested by the manufacturer. Intravenous formulation of ACZ will be stored as lyophilized powder at the temperature specified above in the Hermann Research pharmacy. Lyophilized powder will be reconstituted prior to infusion by the pharmacy. All study medication will be stored at the Hermann Research pharmacy and dispensed as needed during study.

TREATMENT

Rationale for Selection of Dose

The ACZ challenge test, using 1000 mg IV ACZ, is a commonly utilized clinical tool in evaluating patients with chronic intracerebral occlusive disease and is a reliable predictor of critically reduced cerebral perfusion (Vagal et al., 2009). Oral doses as high as 4000 mg daily have been previously used in the NORDIC clinical trial (NORDIC Idiopathic Intracranial Hypertension Study Group Writing Committee et al., 2014).

Participants in this study will be treated with the highest tolerated dose of oral ACZ extended release capsules shown to exert the greatest effect on cerebral perfusion. This dose will also be utilized for an anticipated subsequent large phase 3 trial to determine clinical efficacy.

Study Drug Formulations

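### Stage 1b cerebral blood flow is read by an analyst who knows the dose, although coded, shuffled reading of the completed scan set is feasible and already used in Stage 3

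*Combined protocol and SAP*

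**What the plan says.** **Stage 1b reading.** Under Study Design, Stage 1b, the plan states "Image analysis will be performed once each subject completes treatment" and then "Cerebral perfusion measures will be determined for each dose by the same unblinded analyst". The same analyst reads Stage 1a, where the only reason given is "As all subjects will be treated with IV ACZ, the image analyst will be unblinded during this stage".

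**Use of the readings.** Stage 1b is meant "to define the optimum dose(s) for additional studies". Under Treatment, Rationale for Selection of Dose, the dose carried forward is the highest tolerated one "shown to exert the greatest effect on cerebral perfusion". The Stage 2b schedule table takes its dose from Stage 1b. The Primary & Key Secondary Objective section compares baseline with each escalation step by paired tests, against a CBF increase of at least 15%.

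**Masking elsewhere.** For Stage 3, the Study Design section says "Each subject scan will be assigned a random five-digit number", and Randomization and Blinding repeats the random-ID rule. One Stage 3 rater, "blinded both to treatment arm and sequence of scan acquisition, will perform quality control checks of software segmentation". The Stage 3 text under Rationale for Study Design also says that MRI analysts will not be told the scan sequence. The Blinding paragraph under Treatment calls Stages 1a to 2b unblinded.

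**The concern.** Giving every subject the drug means that there is no treatment arm to mask. It does not explain why the reader must know which scan is baseline and which follows each dose. In a within-subject design that is the contrast that needs masking. The doses rise in a fixed order, so a reader who knows the dose also knows the visit.

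Stage 1b has no concurrent control, and its evidence is the difference between a subject's own scans. A tendency to read on-drug scans higher adds directly to the apparent CBF rise. If the tendency strengthens with dose, it also favours the higher doses in a comparison that helps to set the dose for later stages. No section provides a masked reading, a second reader or a fully automated pipeline for Stage 1b.

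**Working it through.** The plan states no reader-error figure and no power for Stage 1b, so there is nothing to reproduce. The check has two parts.

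**1. Is masking feasible, and do the readings matter?**

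- *Timing:* all of a subject's Stage 1b scans exist before any is read, so they can be shuffled without delay.
- *Tools:* random five-digit IDs and concealed scan order are already specified, but for Stage 3. Using them here extends a procedure.
- *Reader input:* the Stage 3 text describes its imaging measures, CBF among them, as manual and semi-automatic. The Stage 1b text does not say how CBF is extracted. Operator influence is possible but not quantified.
- *Weight:* the readings feed the 15% endpoint and the definition of dose.

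**2. What could a shift do? (illustration only)**

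Inputs:

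- n = 10, the Stage 1b maximum in the Trial Schedule.
- SD of change 30%, borrowed from the Stage 3 calculation in Sample Size and Statistical Methods. I also show 15%, as an assumption.
- Reader shift of 0, 3 or 5 percentage points on drug scans. This is assumed and has no source in the documents.

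*Chance that the observed mean reaches 15%:* 1 − Φ[(15 − true rise − shift) / SE], with SE = SD/√10. That gives 30/√10 = 9.49 and 15/√10 = 4.74.

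| True rise | SD | Shift 0 | Shift 3 | Shift 5 |
|---|---|---|---|---|
| 0% | 30% | 5.7% | 10.3% | 14.6% |
| 0% | 15% | 0.1% | 0.6% | 1.8% |
| 10% | 30% | 29.9% | 41.7% | 50.0% |
| 10% | 15% | 14.6% | 33.7% | 50.0% |

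*Paired t-test, no true effect, 5-point shift:* noncentral t on 9 degrees of freedom, with noncentrality 5/9.49 = 0.53 (SD 30%) or 5/4.74 = 1.05 (SD 15%). The upper-tail rejection rate goes from 2.5% to 6.9% or 15.5%.

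*Dose ranking:* a constant shift cancels between doses. Only a shift that varies with dose matters. I took four dose steps, as in the Stage 1b schedule table, with equal true effects. The within-subject correlation is 0.5 (the Stage 3 value), so the independent error of each dose mean is SD × √0.5/√10, which is 6.71 or 3.35. The reader drift rises linearly from 0 to 5 points. In 100,000 simulated trials the top dose ranked first 39% of the time (SD 30%) or 52% (SD 15%), against 25% with no drift.

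**The case against.** The case on the other side has several parts.

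- **These are small, openly unblinded proof-of-principle stages, followed by a blinded randomized stage.** True. A reader might infer that the trial's main result is compromised. The documents do not support that: the sample-size section takes the 24-week change in Stage 3 as the primary outcome, and Stage 3 images are read blind. The dose-step contrast matters because the objectives section still names it as primary and because it informs dose.
- **The pCASL technique is quantitative, and the wording on manual measurement belongs to Stage 3.** This stands as a limit. It leaves the size of any bias unknown, but the Stage 1b text does not exclude reader influence.
- **The same fault might be read into Stage 1a.** Only partly. Stage 1a gives a single IV dose and does not feed dose selection. Deferred reading is not stated there. The repeat of the scout and 3DT1 sequences at 120 and 240 minutes, and the DSC scan at 240 minutes, may reveal the time point.
- **Masking is not free.** Correct. Someone has to code the scans and hold the key.
- **The consequence for dose is uncertain.** The Stage 2a schedule and the Stage 2b rationale already name a dose, while the Stage 2b table and Rationale for Doses Selected defer to Stage 1b. This is an unresolved conflict in the plan, and it does not justify unmasked reading.

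**Conclusion.** The point holds for Stage 1b. The plan leaves an avoidable route for reader bias in an uncontrolled comparison that carries a 15% endpoint and helps to define dose. It should be corrected.

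The documents do not show that bias will occur, or how large it would be. The percentages above depend on an assumed reader shift and on an SD and correlation taken from Stage 3, and should be read only as a sense of scale. The claim about dose ranking needs the further assumption that the shift grows with dose.

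Masked reading would not cure everything. Dose remains confounded with time in a fixed-order escalation, and a large drug effect may itself hint at which scans are on drug.

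**What to change.** 1. **Study Design, Stage 1b:** replace the unblinded-analyst sentence. Suggested wording: *The random-ID procedure used in Stage 3 also applies to Stage 1b. After a subject's last scan, all of that subject's scans are given to the CBF analyst in random order, without dose, visit or date. Existing study staff other than the analyst hold the key, and dose and visit are linked only after the CBF values are locked.*
2. **Study Design, Stage 1a:** apply the same where practicable, noting that the scan set may partly reveal the time point.
3. **Treatment, Blinding:** amend the statement that Stages 1a to 2b are unblinded, so that it separates open-label treatment from masked image reading. Reconcile it with Data Quality Assurance, which says that all stage 2 data are gathered by raters blinded to treatment.
4. **Dose passages:** reconcile the passages that already name a dose for Stages 2a and 2b with those that defer to Stage 1b, so that it is clear what the Stage 1b readings decide.

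The cost is protocol wording plus minor coding and key-holding work, with no extra scans. Reading already waits for the last scan, so there is no added delay. The documents do not say whether Stage 1 scans have been read. If they have, the stored images would allow a coded, shuffled re-reading at the cost of analyst time.
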